## VIII. Statistical Analysis

The data analysis will be "per protocol." Baseline patient demographics and characteristics will be summarized, compared, and appropriate statistical testing will be performed for the continuous and categorical variables. Assuming a non-normal data distribution for this crossover order-randomized study design, the non-parametric Wilcoxon Signed Rank Sum test will be performed with significance interval of 0.05 on all applicable variables. Parametric analytical analogues (e.g. t-test) will be use if the measurements present a normal distribution. Otherwise, for the categorical variables, the Fisher's Exact test will be performed. Data will be compared and graphed accordingly for a visual comparison with accompanied statistical notations.

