Upper airway purge is important to alveolar gas exchange as the gas that is drawn to the respiratory regions of the lungs comes from the dead space or anatomical reservoir created by the flush, in the same way that oxygen conservation masks (re-breathers) can incorporate reservoir bags to reduce the bulk flow requirements from the oxygen source to achieve the same oxygenation effect.  Based on mathematical modeling, physiologic studies and clinical observations, a flow rate of 4 to 8 L·min through Vapotherm's neonatal cannulae, or 25 to 40 L·min through Vapotherm's adult cannulae, would purge the anatomical reservoir of the upper airway in the window of time between breaths. 

Vapotherm's humidification system is specifically designed to tolerate a high back pressure in the humidification cartridge that is generated by passing these flow rates through small bore cannulae that result in the appropriate flow velocities (turbulent energy).  Since 2000, Vapotherm HVNI has been used extensively and has been well studied and the clinical impact of this ventilation effect using Vapotherm's conventional cannula line is well described  A multi-center recent randomized clinical trial also demonstrated the noninferiority of HVNI to NIPPV in the treatment of undifferentiated respiratory distress for patients presenting to the Emergency Department.  As Vapotherm leads the innovation of new cannulae for the purpose of HVNI, we seek to evaluate the ability of these cannulae to impact ventilatory work effort on dyspneic patients. The goals of the current study are to: (1) evaluate if next generation dual prong (Prosoft) cannulae provide comparable dyspneic relief among hypercapnic adults with accompanying dyspnea compared to current legacy (control) cannula design, and (2) assess if next generation Solo (Unicorn) cannulas at lower flows provide comparable dyspneic relief among hypercapnic adults with accompanying dyspnea compared to current legacy to Dual-prong cannula (Prosoft) design.

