## **II. Overall Study Objective**

The **overall objective** of this study is to evaluate the ability of HVNI next generation Prosoft nasal cannula designs to effect ventilation and related physiological responses relative to the conventional legacy cannula design, with which there are published clinical outcomes data.

The **hypothesis**: The next generation nasal cannula designs (Prosoft and Unicorn) will be comparable at relieving patient dyspnea while on HVNI, when compared to the conventional legacy cannula.

To test this hypothesis, the study will be conducted with the following specific aims:

Aim #1: Primary Outcome. The primary endpoint is the patient's targeted relief of dyspnea, as measured by the modified Borg scale (rated perceived dyspnea [RPD]) for each cannula design tested.

Aim #2: Secondary Outcomes. The secondary endpoints evaluate the patient vital signs (heart rate [HR], respiratory rate [RR], blood pressure [BP]), arterial oxygen saturation (SpO2), and arterial CO2 as measured by a transcutaneous CO2 device (TcPCO2). These measurements will be compiled for each cannula design tested.

Aim #3: Tertiary Outcomes. The tertiary endpoints evaluate both patient and clinician perception assessment scores. For patient perception/satisfaction these endpoints include: (1) relief of symptoms, and (2) comfort/tolerance. For clinician perceptions these endpoints include: (1) technical/clinical difficulties, (2) patient comfort & tolerance, (3) ease of use, (4) monitoring & support for therapy, and (5) expected/perceived patient outcomes.

These **endpoints** will establish equivalence of outcomes between the legacy cannula and the new cannula designs (both Unicorn and Prosoft) in terms of the ability to relieve dyspnea in adult hypercapnic patients experiencing dyspnea.

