## IV. Study Design

This will be an efficacy study, performed as a prospective, order-randomized crossover design trial to evaluate the ability of next generation HVNI nasal cannula designs (Unicorn and Prosoft) to effect ventilation and related physiological responses relative to the conventional legacy cannula design. Patients deemed to fit the criteria for inclusion will perform the study procedures for both arms of the crossover design. Completing both arms will compare the next generation cannula designs to the commonly used legacy design for comfort, comparative therapeutic response, and outcomes per the study aims. Patients are expected to complete the study in one session, with appropriate pauses between each nasal cannula design testing procedures. After each of the study arms, the clinicians will complete perception score assessments. The clinical management will otherwise remain unchanged based on site standard of care practice.

Each phase of the study will correspond to a different cannula design. Patients will be enrolled and initially entered into the control/baseline phase with the conventional legacy cannula (control), then will be order randomized to either of the next generation cannula designs (Test: Unicorn, or Prosoft).

- Phase 1 – Conventional Legacy cannula design (Control)

- Phase 2 Next generation cannula design (Test#1) (order randomized)
- Phase 3 –Next generation cannula design (Test#2) (order randomized)

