This study design will focus on four distinct segments for each phase: (1) baseline characterization, (2) therapy acclimatization, (3) therapeutic characterization, and (4) VAS for both patient and clinician assessment scores. The baseline characterization for Phase 1 will provide patient background, history, and initial clinical evaluation. For Phases 2 and 3, baseline characterization will only include the initial clinical evaluation, as no further initial evaluation is warranted. The acclimatization period will provide patients time to become accustomed to the HVNI therapy and both designs of nasal cannula design. Titration of therapy (Flow/FiO2) is only expected during Phase 1 (or in the event the patient decompensates and needs adjustment), the legacy cannula, as this study is a comparison of cannula efficacy. For the therapeutic characterization, final patient data for the cannula design will be recorded. Following this, the clinician and the patient will complete the cannula design's VAS perception scores. Primary and secondary outcomes will be completed at the end of each individual phase.

This study will be conducted in an inpatient hospital setting where patient testing can be performed with appropriate medical supervision and staff training to maintain patient safety. All respiratory interventions will be tracked during the study window for each patient.

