#### Screening, Enrollment, & Management

Upon screening, subjects will be asked to participate in this study, and if so, they will provide informed consent prior to enrollment. During screening, patient will be evaluated for nostril aperture areas, which will accommodate the various cannula designs without occluding greater than 50% of the aperture area of a nostril by any cannula design (per inclusion criteria #2). Subjects are instructed that if at any time during the study that they wish to discontinue the study, they are free to stop the test and discontinue study participation. All study procedures will be explained to the subject.

Upon enrollment, appropriate study data will be collected (see below under Data Collection), including patient demographics (e.g. age, gender, ethnicity, race), anthropometrics (e.g. weight, height, BMI, and applicable medical history including a detailed focus on the patient's current respiratory status (LTOT user, positive-airway pressure therapy user, current respiratory therapy). Subjects will be managed by routine care while study data is captured as shown in the timeline below (Table 1). All decision making for patient participation will be made per standard practice at the trial site, relying on the judgment of the medical staff. Using cards coded to trial patient number, the two next generation test cannulae will be order-randomized and that randomization will be determined by the clinician or study staff opening sequential numbered opaque envelopes directing such randomization. Time required from screening to the end of the study, is estimated to be two hours and fifteen minutes.

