## VII. Data Collection

## Table 1. Key study data and collection points for each Phase of the Study.

	Baseline Characterization	Therapy Acclimatization	Therapeutic Characterization	@ Study End
Patient History & Health	Х			
Treatment: Flow & O2	Х	Х	Х	
Physiologic Parameters	Х	Х	Х	
Ventilation Parameters	Х	Х	Х	
Clinician Perception Scores			X	Х
Patient Perception Scores			Х	Х

Patient enrollment data collection will include patient history, health, demographics, and current respiratory therapies. Only Phase 1 will record the patients' history and background information. For each segment of each phase, the following data will be recorded for comparison:

Physiologic Parameters o SpO2, HR, RR, BP Ventilation Parameters o RPD, TcPCO2

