## **Primary Endpoint**

• Modified Borg scale score(s) -Rated Perceived Dyspnea (RPD)

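### Prosoft versus Unicorn: the planned paired tests leave out the randomised cannula order, and a sequence term would be a cheap gain in precision

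*Combined protocol and SAP*

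**What the plan says.** **Analysis.** Section VIII states: "Assuming a non-normal data distribution for this crossover order-randomized study design, the non-parametric Wilcoxon Signed Rank Sum test will be performed". A t-test replaces it if the measurements look normal, and Fisher's exact test covers categorical variables. The analysis is per protocol. No section adds a term for order, sequence or period.

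**Order.** Section IV has patients "initially entered into the control/baseline phase with the conventional legacy cannula (control), then will be order randomized" to the new designs. Under Screening, Enrollment, & Management, cards coded to the patient number and held in numbered opaque envelopes decide how "the two next generation test cannulae will be order-randomized". The allocation method (simple or blocked) is not stated. Order is not an item in Table 1.

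**The contrast.** The hypothesis in Section II sets each new cannula against legacy. The second goal in Section I has Unicorn at lower flows "compared to current legacy to Dual-prong cannula (Prosoft) design". The wording is garbled, but it appears to make Prosoft a comparator for Unicorn.

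**The variable.** Section II says "The primary endpoint is the patient's targeted relief of dyspnea", Section VII lists "Modified Borg scale score(s) -Rated Perceived Dyspnea (RPD"), and Section IV says "Primary and secondary outcomes will be completed at the end of each individual phase". Section VII adds: "For each segment of each phase, the following data will be recorded for comparison". RPD is among those data, so each phase has a baseline, an acclimatization and a final reading. The note under Phase 2 lets flow be raised, after data are recorded, when relief is judged not comparable. The final reading then comes after that increase.

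**The concern.** The order of the two new cannulas is the only thing this trial randomises, yet the planned tests do not use it. Dyspneic, hypercapnic inpatients are tested in one sitting, with about two and a quarter hours from screening to study end and usual care continuing. A shift in dyspnea between Phases 2 and 3 is therefore plausible, though nothing in the documents shows one.

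Such a shift enters the Prosoft-minus-Unicorn difference with opposite signs in the two orders. With balanced orders it cancels in the mean but inflates the variance. With unbalanced orders part of it stays in the mean. Imbalance can arise by chance, or from per-protocol exclusions even if allocation was blocked. The stated aim is comparability, so what is at stake is the width and centring of the interval for this contrast.

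**Working it through.** **Inputs from the documents** (Section V, Sample Size): n=26, difference 2, SD 3 (2 to 3 considered suitable), power 90%, alpha 0.05, paired t-test. I take SD 3 as the SD of the paired difference and the test as two-sided.

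**Assumed:** the Phase 3 minus Phase 2 shift π (0, 1 or 2 points), and simple 1:1 randomisation where split probabilities are given.

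**1. The plan's own figure.** Noncentrality = 2×√26/3 = 3.40 on 25 df, which gives power 0.904. N=26 reproduces, and 26×1.2 = 31.2 rounds up to 32.

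**2. Model.** Let D be Prosoft minus Unicorn RPD and τ the cannula difference. The mean of D is τ+π if Prosoft is in Phase 3 and τ−π if it is in Phase 2.
- Planned paired analysis: the mean of D estimates τ + π(n₁−n₂)/n. Its sample variance is about 9 + π²×26/25 at 13:13.
- With a sequence term coded ±0.5: τ is estimated by the average of the two sequence means, with SE = (SD/2)×√(1/n₁+1/n₂) on 24 df. The shift drops out at any split.

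**3. Results at SD 3** (100,000 simulated trials per case):

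| Split | Shift | t-test | With sequence term |
|---|---|---|---|
| 13:13 | 0 / 1 / 2 | power 0.91 / 0.88 / 0.81; half-width 1.20 / 1.27 / 1.45 | about 0.90; 1.20 |
| 16:10 | 1 / 2 | bias 6/26×π = 0.23 / 0.46; type I error 5% / 6% | no bias; 5% |
| 18:8 | 1 / 2 | bias 10/26×π = 0.385 / 0.77; type I error 8% / 15% | no bias; 5% |

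Half-widths are simulation means. The plug-in value at shift 0 is 2.06×3/√26 = 1.21. The signed-rank test behaves like the t-test: power 0.89 / 0.87 / 0.78 at 13:13, and type I error 8% / 15% at 18:8.

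**4. How likely is imbalance?** From the binomial (26, 0.5), a split of 18:8 or worse has probability 0.08, and 16:10 or worse has 0.33. Averaged over random splits at shift 0 / 1 / 2, t-test type I error stays at 5% and power is 0.90 / 0.87 / 0.78, against 0.89 throughout with the term.

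**5. Cost when there is no shift.** At 13:13, SE = 1.5×√(2/13) = 0.588 and power is 0.90. At 16:10, SE = 1.5×√(1/16+1/10) = 0.605 and power is 0.89. At 18:8, SE = 1.5×√(1/18+1/8) = 0.637 and power is 0.85. The t-test without the term has 0.90 in all three.

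**6. SD 2.** At 13:13 and shift 2, power is 0.98 against 0.998, so little power is at stake. The half-width is still about 1.15 against 0.80.

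**7. Adding the phase-baseline RPD difference.** If r is its assumed correlation with the outcome difference, residual SD = 3×√(1−r²). At r = 0 / 0.3 / 0.5, power is 0.90 / 0.93 / 0.96 and the plug-in half-width 1.21 / 1.16 / 1.05. But the Phase 3 baseline follows the Phase 2 cannula. In a simulation with 1 point of unequal carryover reaching that baseline and not the final score, the adjusted estimate was biased by about 0.3 to 0.5 points at r = 0.3 to 0.5, against none without the covariate. When carryover also reached the final score, adjustment helped.

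**8. Legacy contrasts.** Take a drift of −0.5 points per phase, balanced orders and no device effect. Prosoft minus legacy then averages (−0.5−1.0)/2 = −0.75, with or without an order term.

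**The case against.** The strongest reply is that this leaves the main analysis untouched. The hypothesis and the equivalence claim in Section II are against legacy, and Prosoft versus Unicorn rests on one garbled sentence in Section I. That stands, and it is why the point is confined to that contrast.

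The size also rests on an assumed shift. Two points equals the protocol's own minimal important difference, and testing pauses for 15 minutes until dyspnea returns to baseline. This makes large shifts less likely. The pause may limit carryover, but it does not adjust for a period shift. When there is no shift and the split is uneven, the sequence term costs some power; that stands too.

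Three stronger readings are tempting, and the documents do not support them.
- *The planned tests are invalid, with 15% type I error.* That figure needs both an 18:8 split and a 2-point shift. Averaged over random orders the error is 5%, and at 13:13 with a shift the t-test is conservative (about 4% and 2% at shifts 1 and 2).
- *Phase-baseline RPD belongs in the primary model.* The Phase 3 baseline is post-treatment, and unequal carryover could bias the adjusted estimate. The word relief in Section II also leaves change from baseline open, so one cannot say that the plan ignores the baseline.
- *Modelling order repairs the comparison with legacy.* Legacy is always Phase 1, so device and period cannot be separated by any model term.

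**Conclusion.** The point holds as a low-cost improvement limited to Prosoft versus Unicorn. Section VIII does not use the randomised order, although the coded cards fix it for every patient. If dyspnea shifts by 1 to 2 points between Phases 2 and 3, a balanced trial gives an interval about 6% to 21% wider than needed (1.27/1.20 and 1.45/1.20). An 18:8 trial gives an estimate off by about 0.4 to 0.8 points. With no shift there is no gain and a small cost. These sizes assume SD 3 for the paired difference, 26 evaluable patients and shifts that the documents do not supply.

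A separate caution concerns the score. The final RPD can follow a flow increase made because relief was not comparable, so on its own it can hide a cannula difference. The reading taken before the increase is already required, so it can be analysed as well.

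**What to change.** In Section VIII:
1. For Prosoft versus Unicorn, analyse the within-patient RPD difference with a sequence term coded ±0.5, and report the estimate with a 95% confidence interval. Keep the signed-rank test as a sensitivity analysis.
2. State that the order is recorded on the CRF.
3. Report a model that also contains the phase-baseline RPD difference as supportive only.
4. Besides the end-of-phase score, analyse the acclimatization RPD recorded before any flow increase, and report the number of re-titrated phases for each cannula.
5. Keep the legacy contrasts as planned, and state that they are confounded with period because legacy is always Phase 1.

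The cost is SAP wording, one CRF item and one degree of freedom, with no added patients or measurements. If there is no shift, power goes from 0.90 to 0.89 at 16:10 or 0.85 at 18:8, and is practically unchanged at 13:13.

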## Sample Size:

To provide a sufficiently powered sample dataset, we will enroll up to 32 subjects to complete this study on nasal cannula designs, with a calculated sample size of N=26 plus a 20% failure/fallout rate. This will provide sufficient data to adequately inform on the study objectives.

This sample size was estimated through use of references that (1) approximated minimal clinical important difference of dyspnea (modified Borg scale) and (2) approximated expected standard deviation of prior datasets measuring dyspnea. Estimated minimal clinical important difference of dyspnea was determined to be a difference value of 2 in modified Borg for dyspnea. In reviewing publications from Roca 2010 and Schwabbauer 2014, it was estimated that a value of 2 to 3 was suitable for the standard deviation of dyspnea for the modified Borg scale. Therefore, for this study, using the paired t-test sample size calculation, with an expected difference of 2, and an expected standard deviation of 3, using a desired power of 90% with alpha=0.05, the sample size is estimated at 26 to show if the data may or may not have any difference.

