NOTE: Should the patient or clinician deem that the therapy is not providing a comparable relief of dyspnea, then after recording the data stated above, proceed to increase titration of the flow until relief of symptoms, with attention to TcPCO2. At this time, the therapy acclimatization segment should be repeated, and data will be appropriately recorded to account for this 'settings' adjustment. This is to understand any difference in cannula efficacy between legacy design and next generation cannula, designs.

Therapeutic Characterization will be performed 5-10 minutes after the therapy acclimatization segment is completed. This will provide the patient sufficient time to receive clinical effect of the HVNI therapy and become sufficiently comfortable with the therapy and cannula. Once the respiratory therapist or other clinician skilled in management of HVNI deems that the HVNI settings are having a therapeutic effect, the following data will be collected (see Table 1): RR, HR, BP, SpO2, TcPCO2 and RPD (Modified Borg scale 0-10). For the RPD, the clinician will record patient scores.

Patient & Clinician Perception Assessment will be performed by the clinician or therapist performing this phase's testing procedures. Immediately following the completion of this phase, as soon as possible, the continuous Visual Acuity Scale (VAS) will be completed for each of the five endpoints for clinician assessment and the two endpoints for the patient assessment. For the patient perception these include: (1) relief of symptoms, and (2) comfort/tolerance. For the clinician perception these include: (1) technical/clinical difficulties, (2) patient comfort & tolerance, (3) ease of use, (4) monitoring & support for therapy, and (5) expected/perceived patient outcomes.

**Upon completion of this phase**, the testing will pause for 15 minutes, until patient has returned to baseline dyspnea, prior to continuing with the next nasal cannula design test. During this pause the patient will not perform known to worsen dyspnea. During the pause the patient will continue with their current oxygen therapy.

Phase 3 - Test #2 (randomized)

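### Section II promises to establish equivalence of both new cannulae with legacy, but the plan contains only tests of difference, with no margin and no rule for concluding equivalence.

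*Combined protocol and SAP*

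**What the plan says.** **Aim.** Section II says that the endpoints "will establish equivalence of outcomes between the legacy cannula and the new cannula designs (both Unicorn and Prosoft"). The hypothesis there is that the new designs "will be comparable at relieving patient dyspnea while on HVNI, when compared to the conventional legacy cannula", with no number attached to comparable. The primary endpoint is relief of dyspnea "as measured by the modified Borg scale (rated perceived dyspnea [RPD]) for each cannula design tested".

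**Analysis.** Section VIII is the whole analysis plan. Its main provision is that "the non-parametric Wilcoxon Signed Rank Sum test will be performed with significance interval of 0.05 on all applicable variables". It adds a t-test if the data look normal, Fisher's exact test for categorical variables, graphs, and a per-protocol analysis set.

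**Sample size.** Section V uses a paired t-test with difference 2, SD 3, power 90% and alpha 0.05, and concludes that "the sample size is estimated at 26 to show if the data may or may not have any difference". The value 2 is introduced as the minimal clinically important difference (MCID) and used as the difference to detect. It is nowhere called an equivalence margin. The SD comes from the statement that "a value of 2 to 3 was suitable for the standard deviation of dyspnea for the modified Borg scale".

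**Which reading.** Section IV says: "Primary and secondary outcomes will be completed at the end of each individual phase". In Section VI (Phase 2, repeated for Phase 3), if relief is judged not comparable, staff are to "after recording the data stated above, proceed to increase titration of the flow until relief of symptoms" and repeat acclimatization. The end-of-phase reading follows.

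**The concern.** The aim is equivalence, but every planned test, and the power, concerns difference. Nothing in the plan connects the two. The only apparent route to calling a new cannula comparable is a p-value above 0.05. That is an inference, because the plan writes down no rule at all.

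Non-significance does not show equivalence. It becomes easier to obtain as completers are lost or scores get noisier, and a per-protocol set can only reduce the number analysed. Without a stated margin, no error rate attaches to a false claim of equivalence, and a margin chosen after the data are seen would carry little weight.

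The reading compared makes this worse. An end-of-phase score taken after flow was raised because relief fell short can look equivalent because of the added flow, not because of the cannula.

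**Working it through.** **Inputs.** From Section V: difference 2 (the MCID), SD 3 (range 2 to 3), power 90%, alpha 0.05, N = 26, enrolment up to 32. Assumptions of this check: SD 3 is the SD of paired differences, differences are normal, and the trial margins shown are illustrative because the plan gives none.

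**1. The plan's own figure.** Paired t-test, noncentrality δ√n/σ = 2 × √26 / 3 = 3.40 on 25 degrees of freedom, two-sided 0.05. Power is 0.892 at n = 25 and 0.904 at n = 26, so N = 26 reproduces as a two-sided test of difference. A one-sided 0.05 test would need only 21.

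**2. What a non-significant result leaves open.** The standard error is 3/√26 = 0.588. The 95% half-width is t(0.975, 25) × 0.588 = 1.21. An observed difference of just under 1.21 is non-significant, yet its upper 95% limit is about 1.21 + 1.21 = 2.42. The 90% half-width is 1.005, so the upper 90% limit is about 1.21 + 1.005 = 2.22. Both exceed the MCID.

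**3. Non-significance against an equivalence rule.** Two one-sided tests (TOST) at 0.05 with margin ±2 conclude equivalence when |mean difference| + t(0.95, n−1) × s/√n < 2. With s = 3 and n = 26 this means |mean difference| < 2 − 1.005 = 0.995. Chance of each outcome:

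| True difference | SD | n | Non-significant | TOST ±2 passes |
|---|---|---|---|---|
| 1 | 3 | 26 | 62.7% | 50.3% |
| 1.5 | 3 | 26 | 31.2% | 20.7% |
| 2 | 3 | 26 | 9.6% | 5.0% |
| 2 | 3 | 20 | 19.3% | 5.0% |
| 2 | 3 | 10 | 53.1% | 4.3% |
| 1 | 2 | 26 | 31.2% | 79.8% |
| 2 | 2 | 26 | 0.2% | 5.0% |

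At SD 2, TOST ±2 is the more lenient rule. What it gains is a fixed error rate at a stated margin, not greater strictness in every case.

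**4. Power to conclude equivalence, n = 26, SD 3.**
- Margin ±2, per cannula: 90.3% if the true difference is 0, and 79.2% if it is 0.5. A signed-rank version, simulated on normal data, gives 88.7% and 77.2%.
- Narrower margins, true difference 0: 59.6% at ±1.5 (45 completers for 90%) and 7.9% at ±1 (99 for 90%).
- Both cannulae at ±2, true differences 0: 0.815, 0.829 or 0.852 at correlation 0, 0.5 or 0.8 between the two comparisons. At correlation 0.5, joint power is 0.886 with 29 completers and 0.901 with 30.
- A stricter one-sided 0.025 (95% interval) at ±2: 80.9% per cannula, with 32 completers needed for 90%.

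**5. Which SD.** If 3 is the SD of single scores, the SD of differences is 3 × √(2(1 − ρ)): 2.32, 3.00 or 3.55 at within-patient correlation 0.7, 0.5 or 0.3. TOST ±2 power is then 99.1%, 90.3% or 74.9%.

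**The case against.** **The MCID of 2 is an implicit margin, and 90% power makes a null result safe.** With SD 3 and all 26 completers, a missed 2-point difference has a chance of 9.6% against 5% under TOST, which is a modest gap. At SD 2 the difference test is the stricter of the two. This stands as a limit on the size of the problem. It does not supply a rule: the plan never uses 2 as a bound, a non-significant interval can extend beyond 2, and the protection falls away as completers are lost.

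**The joint requirement is not clearly the sponsor's.** Section I lists Prosoft and Unicorn as two goals, and words the Unicorn comparator ambiguously. Section II refers to both designs in one sentence. The joint power of about 0.83 matters only if a single claim for both is intended.

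**An equivalence test alone does not make the claim sound.** Legacy is always in Phase 1 and only the new designs are order-randomized, so each comparison with legacy is confounded with period. This stands. By the table above, an assumed period shift of 0.5 points toward zero would raise the TOST false-equivalence rate at a true difference of 2 from 5% to about 21%, and a 1-point shift to about 50%. It is a separate limitation, to be stated beside the equivalence rule.

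**The reading is already named.** Section IV does point to the end of the phase. The issue is then what that reading measures once flow may have been raised.

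**Borg scores are bounded, and ties are likely.** The power figures, including the signed-rank ones, are therefore idealised.

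**Conclusion.** The concern holds and must be fixed before analysis. The tests in Section VIII cannot support the equivalence conclusion in Section II, because there is no margin, no equivalence test and no decision rule. N = 26 is correct for the test the plan names, and the stated 90% is power to detect a difference. It happens also to give about 90% TOST power per cannula, but only at ±2, SD of differences 3 and a true difference of 0.

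The false-equivalence figures (9.6% at full N, 53% at 10 completers) rest on reading non-significance as comparable, on SD 3, on normal differences and on no period or carry-over effect.

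**What to change.** 1. **Section VIII.** Make the primary analysis an equivalence test of each new cannula against legacy. Conclude equivalence only if the 90% confidence interval of the paired dyspnea difference lies wholly inside a pre-stated margin no wider than 2 Borg units. Use a t-based interval, or Hodges-Lehmann with the signed-rank interval and a stated handling of ties. Justify the margin, since ±2 is the entire MCID. If one claim covers both designs, require both to pass; no alpha split is needed.
2. **Primary reading.** Name it. One option already collected is the acclimatization reading at the designated settings, recorded before any increase for non-comparable relief; use the first such reading if the segment is repeated. The end-of-phase score is then supportive, with the number of patients whose flow was raised. If the end-of-phase score stays primary, say that it compares cannula plus any flow increase. Align Sections IV, VI and VII with the choice.
3. **Section V.** Restate power for this test and say that SD 3 is the SD of paired differences.
4. **Limitation.** State that the fixed legacy-first order leaves each comparison open to period effects.
5. **Fallback.** If no margin can be justified, replace the equivalence claim in Section II with estimation of the difference and its confidence interval.

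**Cost.** Wording and a justified margin, with no new data collection. For 90% joint power at ±2, about 30 completers are needed: 36 enrolled by the plan's own convention (30 × 1.2, as 26 × 1.2 = 31.2 gives its 32), or 38 by 30/0.8 = 37.5 (on which the present plan would need 26/0.8 = 32.5, so 33). Otherwise the sponsor accepts about 0.83. Equivalence also becomes harder to claim if the true difference is not near 0 or the justified margin is below 2.
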